5.3 Enrollment/Baseline

Participants or their parent/legal guardian will provide informed consent (or assent). Applicable informed consent from the participant or parent/legal guardian (and assent if applicable) for all participants will be documented. After consent, the participant will be assigned a unique ID by the school nurse or administrator. The school nurse or administrator will collect study-related variables via a spreadsheet using one of two different methods. The school nurse may use AirTable, a system designed by Technology and Data Solutions, or standard excel spreadsheets, which will be sent to the research team. The research team will have access to individual-level data but will not have access to names or other identifiers. While the study team will have access to the consents completed via REDCap, the team will not know which unique ID belongs to which individual.

The following information will be collected from the student at the time of enrollment. Information may be collected directly from the participant, their parent/legal guardian, or via a school nurse. The information will include the following:

- Participant demographics (age, sex, English proficiency, and vaccination status)
- Mitigation data collection including whether the participant was masked or unmasked, and vaccination status (if known)
- Exposure details include when exposure occurred, where it occurred, and if the individual who caused the exposure was masked or unmasked

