5.4 Testing Period

Eligible participants will undergo COVID-19 testing on days 1, 3, 5, and 7 following known SARS-CoV-2 exposure. If a participant is not aware of the exposure until after the day of exposure, testing will begin immediately on the day of exposure awareness and then resume according to the study schedule (see **Table 1** below for examples). Testing will occur at home or at school according to the Instructions for Use. Participants will be asked to report symptoms for during the testing period. Safety and testing results will also be collected. Pending approval from NCDHHS, the number of tests and the test time points may be changed if deemed safe based on analysis of prior data. For example, if these stakeholders agree that the Test to Stay protocol is safe with two tests rather than four, this change in test frequency may be made. When designing this protocol, the study team used a very conservative approach to prevent undue harm to participants. Over the next several weeks and months, the study team will work closely with stakeholders to modify the test time points and total tests performed to identify the optimal testing protocol which is sustainable for schools (time, resources) but also deemed to be safe.

Table 1. Testing Schedule based on knowledge of exposure

Exposure day	Knowledge of exposure day	Testing days
0	0	1, 3, 5, 7
0	1	1, 3, 5, 7
0	2	2, 3, 5, 7
0	3	3, 5, 7
0	4	4, 5, 7
0	5	5, 7

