8.2.1 Primary Analysis

For the primary endpoint the proportion of students/staff with positive COVID-19 test will be reported and the trend by week will be presented in graphical form. To account for the within-school correlation of outcomes, 95% confidence intervals will be estimated for the proportion using a generalized estimating equations approach using a working independence correlation structure.¹²

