This study will evaluate spread of SARS-CoV-2 following known exposure in schools. This information will be critical for determining future policies surrounding COVID-19 testing, quarantine, and mitigation practices in the Kindergarten through 12th grade school environment. Staff and students who participate in this study will provide consent for testing and collection of data on demographic factors, symptoms, quarantine, and test results. The existing partnerships with schools established through the ABC Science Collaborative, a partnership between Duke and University of North Carolina (UNC) faculty and Kindergarten through 12th grade schools in NC, which was formed in the summer of 2020 will be leveraged.

This study will be conducted across multiple age groups of school-age children and staff, multiple educational settings, and multiple different educational cultures to increase the potential generalizability of study results. Additionally, this study aims to prospectively collect real-world data, which otherwise would be unavailable, to guide evidence-based decision- and policymaking surrounding transmission and quarantine.

Study Design

This is a prospective, interventional study with a primary objective of evaluating severe acute respiratory syndrome coronavirus 2 (SARS-CoV-2) transmission following exposure in Kindergarten through 12th grade schools. Participants will be tested with a COVID-19 testing kit that is Food and Drug Administration (FDA)-authorized under an emergency use authorization (EUA) for non-prescription use for both symptomatic and asymptomatic evaluation in children and adults. Participants who consent to participate in this study will be tested at days 1, 3, 5, and 7 following a known COVID-19 exposure on day 0. If a participant does not know of the exposure until more than one day following they exposure, they will be tested on the day they become aware of the exposure and then resume the aforementioned testing schedule (e.g. participant identifies exposure 3 days after the exposure, test on day 3, day 5, and day 7).

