1.3 Endpoints

Primary Endpoints:

- Proportion of students with positive COVID-19 test following known within-school exposure.
- Proportion of staff with positive COVID-19 tests following known within-school exposure.
- Proportion of exposures undergoing the test-to-stay protocol that result in additional transmission.
- Time to test positivity among those exposed to SARS-CoV-2 and undergoing the test-to-stay protocol.

Secondary Endpoints:

- Secondary #1
 - Proportion of students with positive COVID-19 test following known within-school exposure.
 - Proportion of staff with positive COVID-19 tests following known within-school exposure.
 - Proportion of exposures undergoing the test-to-stay protocol that result in additional transmission.
 - Time to test positivity among those exposed to SARS-CoV-2 and undergoing the test-to-stay protocol.
- Secondary #2
 - Proportion of students with positive COVID-19 test after indoor vs. outdoor exposure.
 - Proportion of students with positive COVID-19 test after athletic vs. classroom exposure.
 - Proportion of students with positive COVID-19 test after bus vs. classroom exposure.
- Secondary #3
 - Total number of school days missed due to symptoms after exposure.
 - Total number of school days missed due to isolation after positive COVID-19 test.
 - Total number of school days missed due to quarantine after SARS-CoV-2 exposure.

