1.4 Handling of Missing Date

For any partially or completely missing date of testing, the scheduled testing day (Day 1, 3, 5, 7) will be used for days to test positivity.

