1.5 Primary Analysis

- Objective: The proportion of students/staff with positive COVID-19 test following known within-school exposure and the proportion of exposures undergoing the test-to-stay protocol that result in additional transmission will be summarized overall, by student or staff, by school district, by school level.
 - To account for the within-school correlation of outcomes, 95% CI will be estimated for the proportion using a generalized estimating equations approach using a working independence correlation structure (Zeger et al. 1988).
 - Objective: Days to test positivity among those exposed to SARS-CoV-2 and undergoing the test-to-stay protocol will be summarized by median and interquartile ranges and nonparametric estimate of test positivity probability will be plotted.

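### Days to test positivity (SAP 1.5) is never reported by first test day, so delay in learning of an exposure is mixed with time to positivity; the missing-date rule in SAP 1.4 omits first tests on days 2 and 4

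*SAP*

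**What the plan says.** SAP 1.3 lists among the primary endpoints "Time to test positivity among those exposed to SARS-CoV-2 and undergoing the test-to-stay protocol". SAP 1.5 says that days to positivity "will be summarized by median and interquartile ranges and nonparametric estimate of test positivity probability will be plotted". It names no estimator, entry time or censoring rule. The breakdowns in SAP 1.5 ("will be summarized overall, by student or staff, by school district, by school level") belong to the proportions. SAP 1.6 repeats the primary analysis by masking of the participant and by masking of the source. SAP 1.7 allows exploratory subgroups but names none.

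Testing does not start on the same day for everyone. For a participant who learns of the exposure late, Protocol 5.4 says "testing will begin immediately on the day of exposure awareness and then resume according to the study schedule". Its Table 1 gives these test days:

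| Learns of exposure on day | Test days |
|---|---|
| 0 or 1 | 1, 3, 5, 7 |
| 2 | 2, 3, 5, 7 |
| 3 | 3, 5, 7 |
| 4 | 4, 5, 7 |
| 5 | 5, 7 |

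The Study Design section of the SAP repeats the rule ("they will be tested on the day they become aware of the exposure and then resume the aforementioned testing schedule"). For a missing test date, SAP 1.4 says "the scheduled testing day (Day 1, 3, 5, 7) will be used for days to test positivity".

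**The concern.** A participant first tested on day 4 cannot be recorded as positive on day 1 or day 3, whatever the course of infection. Days to positivity, counted from exposure, therefore contains two delays: the time until a test would turn positive, and the time until the participant learned of the exposure and was tested. A summary that ignores first test day cannot separate them, and splitting by masking does not separate them either.

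The second delay matters because Protocol 5.4 intends to revise the number and timing of tests to arrive at the best workable schedule. The yield of the early tests is direct evidence for that decision, and it is the part of the curve that late starts distort.

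The missing-date rule has a related gap. Table 1 requires some first tests on days 2 and 4, and neither day is on the list in SAP 1.4.

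**Working it through.** The plan gives no figure for this endpoint to reproduce, and no sample size calculation (Protocol 8.3). It gives no counts by first test day and no number of missing dates. The inputs below marked as assumed are illustrations.

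**1. Formulas.** Take shares among those who test positive by day 7. Assume that an infection once detectable stays detectable through day 7, and that first test day is unrelated to timing. Let p1, p3, p5, p7 be the shares first positive on each day if everyone were tested from day 1. Let L be the fraction of positives first tested after day 1, and L45 the fraction first tested on day 4 or 5. From Table 1:

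- A day-2 starter moves a day-1 positive to day 2, and a day-3 starter moves it to day 3.
- A day-4 starter moves day-1 and day-3 positives to day 4, and a day-5 starter moves them to day 5.
- Recorded day-1 share = p1 × (1 − L).
- Recorded share by day 3 = (p1 + p3) × (1 − L45).
- Shares by days 5 and 7 are unchanged, because every schedule tests on both days.

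The extra test on day 2 (or day 4) may find a fraction q of those otherwise found on day 3 (or day 5). The mean shift per starter is p1 − q·p3 (day 2), 2·p1 (day 3), 3·p1 + p3 − q·p5 (day 4) and 4·p1 + 2·p3 (day 5). A later mean is therefore certain only for day-3 and day-5 starters.

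**2. Two assumed profiles, late starters spread evenly over days 2 to 5 (so L45 = L/2).** Profile A has p = 40/30/20/10%. Profile B has p = 10/20/30/40%. The range for the mean covers q from 0 to 1.

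| Profile | L | Day-1 share | Share by day 3 | Median | Mean later by (days) |
|---|---|---|---|---|---|
| A | 0 | 40% | 70% | 3 | – |
| A | 20% | 32% | 63% | 3 | 0.22–0.25 |
| A | 40% | 24% | 56% | 3 | 0.44–0.49 |
| A | 60% | 16% | 49% | 4 | 0.66–0.74 |
| B | 0 | 10% | 30% | 5 | – |
| B | 20% | 8% | 27% | 5 | 0.06–0.08 |
| B | 40% | 6% | 24% | 5 | 0.11–0.16 |
| B | 60% | 4% | 21% | 5 | 0.17–0.24 |

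For A at L = 40%: 0.40 × 0.6 = 0.24, and 0.70 × 0.8 = 0.56. The share by day 5 stays 90% in A and 60% in B.

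**3. Dependence on when the late starters begin (A, L = 40%).** If all begin on day 3, the share by day 3 stays 70%, while the share on day 3 itself rises from 30% to 0.30 + 0.4 × 0.40 = 46%. If all begin on day 5, the share by day 3 falls to 0.70 × 0.6 = 42% and the median moves from 3 to 5.

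**4. A second model.** The day a test would first turn positive is drawn from a lognormal distribution (log-SD 0.5, assumed). In the mixed case 60% learn of the exposure on day 0 or 1 and 10% on each of days 2 to 5. With a true median of day 3, the reported median goes from 3 to 5 and the share by day 3 from 52% to 42%. With a true median of day 4 or 5, the reported median is 5 throughout, but the share by day 3 still falls from 33% to 26% and from 21% to 16% or 17%. Each fall agrees with the factor 1 − L45 = 0.8.

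**5. Does an interval-censored estimate repair this?** Simulated contacts: 400,000, of whom 5% turn positive; 25% of these are detectable by day 1 and a further 12.5% on each of days 2 to 7; 40% are late starters spread over days 2 to 5.

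| Cumulative positivity | True | Pooled | Interval-censored |
|---|---|---|---|
| By day 1 | 1.255% | 0.749% | 1.253% |
| By day 3 | 2.512% | 1.997% | 2.515% |

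All three agree at days 5 and 7. The repair works here because the simulation meets both assumptions in step 1.

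**6. Missing dates.** Every test day in Table 1 is 1, 3, 5 or 7 except the first test of a day-2 starter and of a day-4 starter. The nearest listed days are 1 or 3 for the former and 3 or 5 for the latter, an error of one day in either direction.

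**The case against.** The strongest reply is that the endpoint concerns people going through the protocol, and starting on the day of awareness is part of the protocol. Pooled time from exposure to first positive is then a coherent description, and no test or decision rule depends on it. This stands: the pooled figure is not wrong for that question. It falls short only for the yield of early tests.

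The wording of SAP 1.5 also does not exclude an interval-censored curve. That stands for the curve, though the estimator should then be named. It does not rescue the median and IQR, and SAP 1.4 treats positivity as falling on an exact day.

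The effect on the planned median is often nil. It is unchanged in five of the six late-start rows in step 2. At L = 20% the IQR is unchanged too (1 to 5 in A, 3 to 7 in B).

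Three stronger readings are tempting, and the documents do not support them:

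- *SAP 1.4 causes errors of two to four days.* A reader might number tests in order, so that a day-5 starter's first test becomes day 1. The more natural meaning is the day on which that participant's test was due, and day-3 and day-5 starters then fit the list.
- *Different testing intensities are pooled.* Protocol 5.4 allows the schedule to change, but nothing shows that it changed in the manuscript #1 population. The weekly plot in Protocol 8.2.1 ("the trend by week will be presented in graphical form") would in any case show such a change only in part.
- *The timing results are materially wrong.* Without first-test-day counts the size cannot be stated.

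**Conclusion.** The concern holds in a limited form. As planned, days to positivity mixes delay in awareness with time to positivity. Compared with testing everyone from day 1, the day-1 share among positives is too low by the factor 1 − L, and the share by day 3 by the factor 1 − L45. Shares by days 5 and 7 are unaffected. The median moves by zero to two days in the scenarios examined, and often by zero. In SAP 1.4 the error is about one day, and only for a missing first-test date on day 2 or 4.

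The factors assume that positivity persists through day 7 and that first test day is unrelated to timing. The second assumption could fail, for example if contacts with early symptoms isolate before a late first test and never enrol. L, L45 and the number of missing dates are unknown. The change is worth making because it is cheap and the early part of the curve bears on the choice of test days. It does not call the endpoint itself into question.

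**What to change.** **SAP 1.5.** Derive first test day as first test date minus exposure date, and report its distribution. Give days to positivity (median, IQR, curve) for those first tested on day 1, and separately for later starters, for example days 2–3 and days 4–5. For any overall curve and median, specify an interval-censored nonparametric estimate. The interval runs from last negative to first positive test, or from exposure if the first test is positive. State both assumptions. If a median among positives is wanted, read it where the curve reaches half its day-7 height.

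**SAP 1.4.** Replace the fixed list with the participant's own scheduled day under Table 1. Where awareness day is not recorded, keep the date as an interval between the adjacent dated events, and report how many dates are handled this way.

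**If a schedule change did occur in this population,** also report by schedule in force, as a before–after description. This needs a dated record of each change.

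**Cost.** Wording in two sections and one derived variable; no extra tests or participants. The strata will be smaller, and the day 4–5 group may be sparse. First test day also reflects skipped early tests, not only late awareness. Awareness day is not among the exposure items in Protocol 5.3 ("Exposure details include when exposure occurred, where it occurred, and if the individual who caused the exposure was masked or unmasked"), so some missing first-test dates can only be kept as intervals.

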1.6 Secondary Analysis

- Objective: The proportion of students/staff who reported masking and unmasking will be summarized and presented in a bar chart to see the trend by testing day.
 - The primary analysis will be repeated for masked and unmasked participants (students and staff) separately.
 - The primary analysis will be repeated for masked and unmasked source of exposure separately.
- Objective: School absences will be analyzed by absences due to symptoms, positive COVID-19 test, or due to quarantine for exposure to SARS-CoV-2.
 - To account for the within-school correlation of outcomes, analyses will be conducted using a generalized estimating equations approach using a loglink suitable for count outcomes, with a working independence correlation structure (Zeger et al. 1988).

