5 STUDY PROCEDURES

5.1 Summary of Evaluations

	Enrollment/Baseline	Testing Period	Follow-Up
PROCEDURE	Day 0	Day 1, 3, 5, 7	Up to Day 14
Screening	X		
Informed consent/assent	X		
Confirm eligibility criteria	X		
Demographics	X		
Mitigation data collection	X		
Exposure information	X		

COVID-19 testing and results collection		X	
Symptom data		X	X
Safety Assessment		X	

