5.5 Follow-Up

Participants will be asked to report symptoms for up to 14 days following SARS-CoV-2 exposure. Schools will be asked to report tertiary spread and number of close contacts for individuals who tested positive.

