If the COVID-19 tests are negative, the participant will remain in the school environment. A positive COVID-19 test or the development of symptoms on any day after exposure would require isolation according to school, local and state guidelines. Demographic information, daily presence or absence of symptoms, whether the infected person or close contact was masked, setting of the exposure, test results, and school absences will be collected following consent. Data regarding school level mitigation practices will also be collected. Data collected from this study may be combined with school-provided data and publically available community data.

General Statistics Principles

In summary tables of continuous variables, the mean, median, interquartile ranges, 95% confidence interval (CI), standard deviation and standard error will be presented to one more decimal place than the original data. In the event no meaningful information is available through the aforementioned decimal place, the statistician in consultation with the PI or designee will determine the most relevant number of decimals to display. Summaries of continuous characteristics will be based on non-missing observations.

In summary tables of categorical variables, counts and percentages will be used. The denominator for each percentage will be the number of participants with non-missing values and without 'Unknown' or 'Prefer not to answer/say' for the variable within the population treatment group unless otherwise specified.

All statistical analysis will be performed using SAS® v9.4 or higher (Cary, NC USA). Other software may be used if required and determined to be appropriate.

Quality Assurance Procedure:

Each table shell and figure legend specifies what steps will be performed to ensure quality results. Based on the complexity of project specific analyses or generating analysis data sets, double programming or code review by another programmer/statistician may be implemented.

Manuscript #1 COVID-19 Testing Following Exposure in School Communities

Date	June 27, 2022
Corresponding author	[name], MPH
Lead statistician	[name]
Statistical advisor	[name]
Project leader	[name]
Target journal	TBD

History of changes

Date	Version	Summary of changes

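### SAP 1.6 charts masking by testing day, but the documents describe a single mask value per participant, taken at enrolment; the chart, one split and the Secondary #1 endpoints need rewording

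*SAP*

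**What the plan says.** **The chart.** SAP 1.6 (Manuscript #1) says that the proportion reporting masking and unmasking "will be summarized and presented in a bar chart to see the trend by testing day". Protocol 8.2.2 asks for the same proportion in a graph and gives no time axis.

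**When masking is recorded.** In the schedule in Protocol 5.1, the row "Mitigation data collection" is marked under Enrollment/Baseline only. Protocol 5.3 opens its list with "The following information will be collected from the student at the time of enrollment", and the list includes "Mitigation data collection including whether the participant was masked or unmasked". The SAP's Study Design section, like Protocol 3.1, lists "daily presence or absence of symptoms, whether the infected person or close contact was masked, setting of the exposure" among the data; the word for daily attaches to symptoms. For the testing period, Protocol 5.4 says "Participants will be asked to report symptoms for during the testing period. Safety and testing results will also be collected". For follow-up, Protocol 5.5 adds "Schools will be asked to report tertiary spread and number of close contacts for individuals who tested positive". Neither section lists a mask item.

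**The splits.** SAP 1.5 includes additional transmission in the primary analysis. SAP 1.6 repeats that analysis by participant masking and, separately, by masking of the source of exposure.

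**The endpoints.** Protocol 8.1.2 defines Secondary #1 as four endpoints on test positivity: masked students, masked staff, unmasked students and unmasked staff, each by masked versus unmasked source. SAP 1.3 Secondary #1 instead lists the four primary endpoints again.

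**The concern.** A bar chart of masking over Days 1, 3, 5 and 7 invites the reader to see behaviour: participants keeping masks on, or taking them off, as the testing period goes on. A single enrolment value cannot carry that information. A rise or fall would be a change in who was tested, and a flat chart would say nothing about adherence.

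A similar misreading threatens the additional-transmission split. In onward spread the participant is the possible source, so a masked-versus-unmasked difference could be taken as the effect of masking while infectious. The recorded item describes an earlier moment.

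Finally, with Secondary #1 overwritten in SAP 1.3, the cross of participant masking with source masking, which is the protocol's own content for its masking objective, has no listed endpoint and no described table.

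**Working it through.** The plan gives no figure on this point, so there is none to reproduce. The check compares the planned outputs with the collection described.

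**1. Values per participant.** Mitigation data are marked in 1 of 3 schedule columns, so there is 1 mask value per participant. Testing days under the initial schedule are 1, 3, 5 and 7 (Protocol 5.4; SAP 1.4 uses the same list), so that value feeds up to 4 bars.

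**2. What the chart can show.** Let m_i be the recorded mask value (1 or 0) of participant i, R_t the set tested on day t, and n_t their number.

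share_t = (sum of m_i over R_t) / n_t

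Since m_i does not depend on t, share_t − share_s = 0 whenever R_t = R_s. Among participants tested on all four days the trend is exactly 0 by construction. Any non-zero difference comes from a change in R_t.

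**3. Whether R_t changes.** It does, for two documented reasons.
- Late awareness: "testing will begin immediately on the day of exposure awareness". In Table 1 of Protocol 5.4, awareness on day 0, 1, 2, 3, 4 or 5 gives a first test on day 1, 1, 2, 3, 4 or 5. The first test falls after Day 1 in 4 of 6 rows. Rows with a test on Days 1, 3, 5 and 7 number 2, 4, 6 and 6 of 6. These are rows of an example table, not participants.
- Exit: a positive test or symptoms leads to isolation (Protocol 3.1), and Protocol 3.3 gives both as reasons for incomplete testing.

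**4. Illustration on assumed inputs (none from the documents).** Start with 70% masked on Day 1, no late entry, and removal after each test of 5% of masked and 15% of unmasked participants.
- Day 3: 0.70×0.95 / (0.70×0.95 + 0.30×0.85) = 0.665/0.920 = 72.3%
- Day 5: 0.6318/(0.6318 + 0.2168) = 74.5%
- Day 7: 0.6002/(0.6002 + 0.1842) = 76.5%

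The chart rises 6.5 points although nobody changed behaviour. For starting shares of 50% to 90% and the removal rates tried (2% masked with 2%, 6% or 10% unmasked; 5% with 15%), the Day 1 to Day 7 change ran from 0 to about 8 points. Conversely, with no removal, if 60% of those masked at enrolment stop masking by Day 7, the true share is 70×(1 − 0.60) = 28% and the chart still shows 70%.

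**5. The additional-transmission split.** The endpoint is per exposure:

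P(additional transmission) = P(participant infected) × P(onward spread | infected)

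Masking at the index exposure bears directly on the first factor, so the split is meaningful for the whole chain. It does not measure masking during the second. As an assumed example, let the risk depend only on masking while infectious: 2% masked, 6% unmasked, ratio 3.0. If recorded status matches that status 80% of the time, the split shows 0.8×2 + 0.2×6 = 2.8% against 0.8×6 + 0.2×2 = 5.2%, ratio 1.86. At 50% agreement both are 4% and the ratio is 1.0.

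**6. Secondary #1.** The protocol's endpoints need 2 participant statuses × 2 source statuses = 4 cells in each role, 8 over students and staff. SAP 1.6 gives the two masking factors one at a time, and one-way summaries do not determine the cross. Protocol 8.2.2 also describes only the one-way repeats, so the endpoint list is the only place where the cross is specified.

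**The case against.** **The schedule is incomplete.** It has no row for absences, tertiary spread or number of close contacts, yet Protocol 3.1 and 5.5 collect them. Silence about repeated masking is therefore weak evidence. Protocol 13.4 lists mitigation practices without timing, the spreadsheet and AirTable fields are not shown, and the Manuscript #1 section is dated June 27, 2022, when its authors may have known which fields existed. This stands as a limit. A reader might infer that masking during the testing days was definitely not recorded; the documents show only that no such item is described.

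**Testing day is undefined in SAP 1.6.** It could mean calendar date, in parallel with the weekly trend in Protocol 8.2.1. One value per participant would then support a trend across participants. The scheduled-day reading is more natural, since SAP 1.4 uses the term for Days 1, 3, 5 and 7, but the conclusion is conditional on it.

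**The split is legitimate.** A reader might infer that splitting additional transmission by participant masking is invalid and should be dropped. The documents do not support that: the endpoint is per exposure, index-exposure masking affects its first step, and the SAP never calls this split source masking. What remains is the need for a label.

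**Was masking mandatory after exposure?** A reader might infer that both groups were masked on later school days. Protocol 1.1.1 says so only of the strategy in general, and Protocol 1.4 mentions masking requirements without detail. Protocol 4.1.2 and SAP 2.2 point to optional masking in some settings. The question is open, and no adherence figures are given.

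**Conclusion.** The point holds in a limited form. On the collection described, and if testing day means Days 1, 3, 5 and 7, the SAP 1.6 chart cannot show a change in masking over the testing period. That the item refers to the index exposure is a reading of the past tense in Protocol 5.3 and of its pairing with the infected person's masking in Protocol 3.1. The additional-transmission split can stay with a label. The replacement of Secondary #1 in SAP 1.3 needs correcting and does not depend on how testing day is read.

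Severity is minor. One descriptive chart, one label and one endpoint list are affected. The masking analyses of test positivity are sound on this point, because masking at the exposure is the relevant status there. The size of any spurious trend or dilution cannot be derived from the documents; the percentages above only illustrate the mechanism.

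**What to change.** - **Chart (SAP 1.6).** Plot mask status at exposure overall, or by calendar week of exposure, which the collected item supports. Alternatively keep the axis, title it *mask status at exposure among those tested on each day*, and print the number tested under each bar. If calendar date was meant, or a repeated mask field exists, say so and name the field.
- **Split (SAP 1.6).** Keep additional transmission by participant masking, labelled *mask status at index exposure; not masking while infectious*.
- **Endpoints (SAP 1.3).** Replace Secondary #1 with the four endpoints of Protocol 8.1.2, and add to SAP 1.6 a table of test positivity by participant masking and source masking, for students and staff separately.
- **Optional, for further enrolment.** Add one yes/no item at each test on mask use in school since the last test.

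For data already collected, the cost is SAP wording and one added table; some cells of the cross may be sparse. The optional item adds a short question per test. Some answers will be missing because tests may be done at home, and where masking is required the item may show adherence only.
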